6.1 Subject-Related Procedures

- *Screening* of volunteers to confirm the diagnosis of PCOS will typically be based on previously measured hormone levels. It is anticipated that most subjects with PCOS will be diagnosed by the PI just prior to study entry, and will likely involve performance of a hormonal evaluation within 6 months of beginning the study. However, the timing of previous hormone measurements used to diagnose PCOS will be left to the discretion of the PI. If the relevant tests for this purpose have not been performed previously, the necessary hormone levels will be obtained from a screening blood draw which will also be used to measure a CBC and CMP (maximum 22 ml). Assays to measure prolactin, TSH, LH, FSH, total testosterone, free testosterone, androstenedione, DHEA-S and 17-hydroxyprogesterone (17OHP) along with the CBC and CMP will be performed by the UI Health Clinical Pathology Laboratory. Pregnancy will be ruled out in all subjects immediately prior to study testing before and after treatment with salsalate or placebo using a urine test sensitive enough to detect >50 mIU/L of HCG.
- *Screening* of volunteers with an OGTT to rule out diabetes and to determine IR status will be performed in the CCTS CRC prior to study entry after an overnight fast of ~12 hours. A polyethylene intravenous catheter will be inserted in an arm vein for blood sampling at ~9:00 AM. The size of the catheter (i.e. 18-23-gauge) will be of suitable caliber for the size of the vein used to gain access. A baseline blood sample (9 ml) will be drawn in the fasting state. A 75 gram glucose beverage will subsequently be ingested over 10 minutes. Blood samples (9 ml each) will again be drawn at 30, 60, 90, 120 and 180 minutes following glucose ingestion. Every attempt will be made to insert the intravenous catheter and obtain blood samples on time. However, a sample may be obtained within a fifteen minute window after the scheduled time due to any unforeseen technical difficulty. Upon completion of the test, the indwelling catheter will be removed and subjects will be fed a high carbohydrate snack. Blood glucose and plasma insulin levels will be measured by the UI Health Clinical Pathology Laboratory.

- A complete medical *History and Physical Examination* will be performed in the in the CCTS CRC. A Pap smear will be performed at the same time only if a volunteer is due for one in accordance with ACOG guidelines. Otherwise, a copy of the most recent Pap smear will be requested after obtaining a signed release of medical information from the volunteer.
- *Vaginal Sonography* to assess ovarian morphology will be performed during the initial screening in the CCTS CRC on the day of the entry history and physical examination. Polycystic ovaries will be defined by published criteria established by Dewailly et al;³⁶ namely, the presence of 25 or more subcapsular follicles measuring 2-9 mm in diameter or increased ovarian volume ($>10 \text{ cm}^3$).
- *Body Composition* will be assessed at the beginning of the study using 2 modalities:
 - *Dual Energy X-ray Absorptiometry* (DEXA, Model LUNAR iDXA, General Electric Healthcare, Wood Dale, IL) will be performed in the IPL at which time anthropometric measures of height and weight will be taken using standard techniques. These measures are required for the DEXA scan. All female participants will perform a spot pregnancy test prior to DEXA scan. If pregnancy test is positive the participant will be excluded. The instrument emits photons at 2 different energy levels as a detection scanner traverses the body. The detected energy passes through the body with differential attenuation that is computer analyzed to calculate body fat. The total fat quantity, and truncal fat quantity will be measured, the latter of which is defined as the area between the dome of the diaphragm (cephalad limit) and the top of the greater trochanter (caudal limit).³⁷ Fat quantity will also be measured in the central abdominal area (R1 area) which is an area of 50 cm² around the central point of the midline between the lateral iliac crests and the lowest rib margins at the end of normal expiration (the same midline used for waist circumference).³⁸ Study subjects will wear light clothing and lie on their backs during the procedure which takes 10-15 minutes to complete. Subjects will be exposed to a radiation dose of $\leq 0.3 \text{ mrem}$ based upon manufacturer's specifications and calculations from Standford Dosimetry, LLC RADAR Medical Procedure Radiation Dose Calculator. A Radiation Safety Committee review is not required for this amount of research protocol radiation exposure given the estimated effective equivalent dose is below 100 mrem (1 mSv) per year, a limit set by the Nuclear Regulatory Commission for "general public" exposure.
 - *Magnetic Resonance Imaging* (MRI, Siemens MAGNETOM Trio 3T, Malvern, PA) will be performed at the Center for Magnetic Resonance Research, [name]. The MRI scanner performs an axial scan in the supine position to measure abdominal adiposity as previously described.³⁹ A gradient echo pulse sequence with water suppression to obtain a fat-only image is followed by lipid suppression to obtain a water-only image and no suppression to serve as an anatomic reference. Five 4 mm slices centered at L3 are obtained and the fat signal intensity ratio [$If/(If+Iw)$] is calculated from the fat-only (If) and water-only (Iw) images on a pixel-by-pixel basis to produce a map. The calibration curve obtained from a previous phantom study is used to convert this ratio to a fat percentage value that is used to determine visceral and subcutaneous fat volumes with AnalyzeDirect, Inc. software (Stilwell, KS).³⁹
- *HCG Stimulation Test (HCG-ST):* The test will be performed in the CRC as described by Piltonen et al.⁴⁰ over three (3) short CRC visits. A baseline blood sample (16 ml) will be

[figure not shown]
drawn after an overnight fast of ~12 hours followed by administration of a single intramuscular injection of 5,000 IU HCG (Pregnyl; Schering-Plough, Kenilworth, NJ). Fasting blood samples (16 ml each) will again be drawn at 24, 48, and 96 hours after HCG administration (*please refer to the Risks - Venipuncture / Venous Catheter Blood Sampling subsection of Section 7.0 for the approach and alternatives to venipuncture*). Every attempt will be made to obtain blood samples on time. However, the baseline sample may be obtained within a fifteen minute window and the post-HCG samples may be obtained within a sixty minute window after the scheduled time due to any unforeseen technical difficulty. Gathering of vital signs during the single blood draw visits will be considered if there is any clinical evidence subject instability. Plasma will be isolated from the blood samples collected and stored at -80° C until assayed for testosterone, androstenedione and 17OHP.

- **Cream Challenge Test (CCT):** All subjects will consume a standard weight maintenance diet consisting of 50% carbohydrate, 35% fat and 15% protein for 3 consecutive days (*days 1 – 3*) before the test through meals prepared by the CRC dietician. The test will be performed in the CRC on the day of the 96 hour HCG-ST blood draw after an overnight fast of ~12 hours as described by Deopurkar et al.⁴¹ A polyethylene intravenous catheter will be inserted in an arm vein for blood sampling at ~8:30 AM. The size of the catheter (i.e. 18-23-gauge) will be of suitable caliber for the size of the vein used to gain access (*please refer to the Risks - Venipuncture / Venous Catheter Blood Sampling subsection of Section 7.0 for the approach and alternatives to intravenous catheter placement*). A baseline blood sample (90 ml each) will be drawn in the fasting state at ~9:00 AM. One hundred (100) ml of dairy cream (gourmet heavy whipping cream; Land O Lakes Inc, Arden Hills, MN) will then be ingested over 10 minutes. This dairy cream preparation has 33 gm of fat and 1257 kJ (300 kcal)/100 ml cream. The saturated fat content of the cream preparation is 70% (28% unsaturated fat), the protein content is <2%, and the glucose content is 0%. Blood samples (80 ml each) will again be drawn at 120, 180 and 300 minutes after cream ingestion. Every attempt will be made to insert the intravenous catheter and obtain blood samples on time. However, a sample may be obtained within a fifteen minute window after the scheduled time due to any unforeseen technical difficulty. Upon completion of the test, the catheter will be removed, and subjects will be fed a study meal for lunch as described above. Subjects will also be discharged with weight maintenance study meals to consume that evening and up until they begin the FS-IVGTT. MNC will be isolated from the blood samples collected and used to measure ROS, or placed in culture, or processed for storage at -80°C until used for RT-PCR, Western blotting and electrophoretic mobility shift assay (EMSA). Plasma will also be isolated from the same blood samples and stored at -80°C until assayed for cytokine levels.
- **Diet Instruction and Monitoring:** All subjects will receive detailed diet instructions from a UIC Department of Medicine registered dietician on the day of the pre-treatment CCT aimed at maintaining a similar weight throughout the study. The instructions will focus on having subjects consume their habitual pre-study food intake throughout the ~12 weeks of treatment. Subjects will complete a 24 hour food record just before entering the study to serve as a guide for the diet instructions. Subjects will subsequently weigh themselves at home on a weekly basis using the same scale to alert the study team if they have lost or gained more than 4 pounds compared with their weight at study entry. The registered dietician will provide additional counseling to these subjects as needed to determine if any diet adjustments are required for weight maintenance. Subjects will also keep a 24 hour food record on a monthly basis that will be reviewed by trained staff from the Nutrition

service to assess compliance. Subjects will return the 24 hour food records to the CRC when they report for each monthly salicylate level blood draw.

- **Insulin-Modified FS-IVGTT:** The test will be performed in the CRC two (2) days after the CCT after an overnight fast of ~12 hours as described by Polidori et al.³² An intravenous polyethylene catheter will be inserted in an forearm vein at ~7:10 AM (-50 minutes) for infusing glucose and insulin. Another intravenous catheter will be inserted in a contralateral forearm vein for blood sampling. The size of the catheter (i.e. 18-23-gauge) will be of suitable caliber for the size of the vein used to gain access (*please refer to the Risks - Venipuncture / Venous Catheter Blood Sampling subsection of Section 7.0 for the approach and alternatives to intravenous catheter placement*). Baseline blood samples will be obtained at ~7:40 AM (-20 minutes), ~7:50 AM (-10 minutes), ~7:59 AM (-1 minute) and ~8 AM (0 minutes). The average of the four samples is considered the basal level. A glucose solution (0.3 gm/kg) will be administered intravenously beginning immediately after the 0 minute blood draw. Insulin (20 mU/kg Humulin; Eli Lilly, Indianapolis, IN) delivered in 1 unit/ml infused over 60 seconds starting at ~8:20 AM (20 minutes). Blood samples will be obtained at -20, -10, -1, 0, 1, 2, 3, 4, 5, 6, 7, 8, 10, 12, 14, 16, 19, 22, 23, 24, 25, 27, 30, 40, 50, 60, 70, 80, 90, 100, 120, 150, 180 and 240 minutes. Every attempt will be made to insert the intravenous catheters and obtain blood samples on time. However, all samples with the exception of those used to measure glucose may be obtained within a fifteen minute window after the scheduled time due to any unforeseen technical difficulty. A total of 272 ml of blood (8 ml/sample) will be collected during the entire procedure. All infusions will be stopped at 12 PM. Upon completion of the test, both catheters will be removed, and subjects will be fed a standard lunch. Plasma will be isolated from the blood samples collected and stored at -80° C until assayed for glucose, insulin, C-peptide and FFA. Preparation of glucose and insulin for infusion during the FS-IVGTT procedure will be performed by the UI Hospital Pharmacy Investigational Drug Services.

- *Mathematical Model to Assess Hepatic and Extrahepatic Insulin Clearance.* Hepatic and peripheral insulin clearances were estimated using a model for insulin kinetics during the FS-IVGTT as described in Fig. 3.

The model is based on the following main assumptions:

1. Endogenously secreted insulin enters the portal circulation where it travels to the liver before reaching the systemic circulation. The insulin secretion rate (ISR) will be calculated by deconvolution using C-peptide kinetic parameters.⁴² The calculated ISR and the known insulin infusion rate will be used as inputs to the model.

2. The rate of delivery of insulin from the systemic circulation to the liver reported in pmoles/minute is equal to the plasma insulin concentration reported in pmoles/liter times the assumed hepatic plasma flow (HPF) rate (0.576 L/min/m²).⁴³
3. Insulin clearance occurs in both the liver and in extrahepatic (peripheral) tissues, which includes kidney, muscle, and adipose tissue. Extrahepatic clearance is assumed to be proportional to the plasma concentration.
4. Hepatic clearance will be modeled using either a linear or a saturable function. Both functions will be tested in each subject, and the one providing the best fit will be retained. Both functions will be considered because some previous studies have suggested linear clearance, whereas others have suggested nonlinear and/or time-dependent clearance.^{30,43-45} No time-dependent changes in parameter values will be modeled.

Given these assumptions, the resulting model requires estimating either three (linear model) or four (saturable) parameters from the measured plasma insulin profiles and calculated ISR.

The following equations and parameters correspond with these main assumptions. The HPF rate used in the equations is the combined plasma flow to the liver from the portal vein and the hepatic artery.

Insulin delivery to liver (pmol/min)

$$\text{Delivery} = \text{ISR} + \text{HPF} \cdot P$$

Hepatic insulin degradation (pmol/min)

$$\text{Linear model} = FE_L \cdot \text{Delivery}$$

$$\text{Saturable model} = \frac{V_{max} \cdot \text{Delivery}}{K_m + \text{Delivery}}$$

$$\text{Extrahepatic insulin degradation (pmol/min)} = CL_P \cdot P$$

P is plasma insulin reported in pmoles/liter, $/SR$ is reported in pmoles/minute, HPF and CL_P are reported in liters/minute, FE_L is hepatic fractional extraction (dimensionless), V_{max} is the maximal hepatic degradation rate reported in pmoles/minute, and K_m is the hepatic insulin delivery rate at which 50% of maximal degradation occurs reported in pmoles/minute.

The differential equations for the linear (Equation 1) and saturable (Equation 2) assumptions are as follows:

$$V_P \frac{dP}{dt} = \text{Infusion Rate} + (1 - FE_L) \cdot ISR - (HPF \cdot FE_L + CL_P) \cdot P$$

$$V_P \frac{dP}{dt} = \text{Infusion Rate} + ISR - CL_P \cdot P - \frac{V_{max} \cdot \text{Delivery}}{K_m + \text{Delivery}}$$

V_P is the extrahepatic distribution volume for insulin reported in liters. Model-identified parameters will be normalized by body weight (BW) for comparison across subjects. For the saturable clearance model, fractional hepatic extraction varies with changes in $/SR$ and P . FE_L values will be calculated in the basal state when compiling parameter summaries.

To provide measures of clearance that are related to analogous measures obtained by other experimental methods, Equations 1 and 2 will be used to calculate measures that would be

estimated from steady-state insulin infusions administered either intravenously as in hyperinsulinemic-euglycemic clamps or in the portal vein as in endogenous secretion. The corresponding clearance values from the model for an intravenous infusion (CL_{IV}) or for a portal infusion (CL_{portal}) will be calculated by dividing the insulin infusion rate by the steady-state plasma insulin concentration. These linear model calculations are summarized as follows:

$$CL_{IV} = CL_P + HPF \cdot FE_L$$

$$CL_{portal} = \frac{CL_{IV}}{1 - FE_L}$$

For the saturable clearance model, the effective clearance parameters vary with the insulin infusion rate, and values will be calculated assuming an infusion rate of 240 pmol/min/m² as commonly used in hyperinsulinemic-euglycemic clamps. The proportion of total insulin degradation occurring in hepatic versus extrahepatic tissues will be calculated by integrating the degradation rates over the 240 minute interval. The insulin sensitivity index (S_I) will be determined from the FS-IVGTT using MINMOD Millenium version 6.02.

- **Ovulation Monitoring:** All subjects will maintain a basal body temperature (BBT) chart throughout the ~12 weeks of treatment after appropriate instructions. A blood sample (5 ml) will be drawn to measure serum progesterone to detect ovulation on the 7th day of temperature elevation of at least ¾°F from baseline indicative of a biphasic BBT response. Subjects will be instructed to alert the team regarding the potential need to schedule a progesterone measurement when 3 consecutive days of temperature elevation is evident. The length of the cycle in which a luteal range progesterone (>2 ng/ml) is documented will be used to time initiation of midcycle urine luteinizing hormone (LH) monitoring with a commercially available kit. Vaginal sonography will be performed in the CRC on the day of the color change signifying the LH surge and the following day to document follicular development and collapse, respectively, as the definitive evidence of ovulation.

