sonography within 21 days of study start reveals no evidence of follicular development in the face of a negative pregnancy test.

Visits 1 through 5 will occur during the first week of the study protocol. During Visits 1 through 4, subjects will undergo an HCG stimulation test (HCG-ST) in the CRC consisting of a single IM HCG injection during Visit 1 after documenting a negative urine pregnancy test, along with a single blood draw during all 4 visits at 0, 24, 48 and 96 hours after HCG administration to measure serum androgens and 17-hydroxyprogesterone. Visits 1 through 3 will be short lasting ~30 minutes. After one of these short visits, subjects will also undergo a body composition assessment consisting of a whole-body dual-emission X-ray absorptiometry (DEXA) scan in the Integrative Physiology Laboratory (IPL) at [name], and a magnetic resonance image of the abdomen in the Center for Magnetic Resonance Research at [name]. Visit 4 will last ~8 hours during which a cream challenge test (CCT) will also be performed in the CRC consisting of dairy cream ingestion and serial blood draws at 0, 2, 3 and 5 hours after cream ingestion to measure inflammation markers. Visit 5 will last ~7 hours and occur 2 days after the CCT during which subjects will undergo a FS-IVGTT in the CRC to assess insulin sensitivity and glucose-stimulated inflammation.

[figure not shown]
| Table 1. PRE-STUDY SCREENING | | | | |
|--|---------|---|---|---|
| STUDY PROTOCOL | WEEKS → | 0 | 4 | 8 |
| Salicylate Level | | X | X | X |
| Sex Hormone Binding Globulin | | X | | X |
| Body Composition: MRI & DEXA | | X | | |
| HCG Stimulation Test: T, A & 17OHP @ 0, 24, 48 & 96 hours. | | X | | X |
| Cream Challenge Test: MNC-derived ROS, NFκB, RNA & protein inflammat'n markers @ 0, 2, 3 & 5 hours. | | X | | X |
| Frequently Sampled Intravenous Glucose Tolerance Test: glucose, insulin, C-peptide & FFA q 1-30 minutes x 34 samples from -20-240 minutes. | | X | | X |
| Post-Study Safety Tests: CBC & CMP. | | | | X |
| Ovulation Monitoring: BBT from 0-12 weeks; P on 7th day of BBT rise; If P >2 ng/dl documented, vaginal sonography on day of & day after LH surge. | | | | |

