A predefined computer-generated randomization schedule set up by a statistician will have centralized allocation and codes secured by a research pharmacist. This schedule will be used to assign recruited subjects to receive salsalate (Amneal Pharmaceuticals, Bridgewater, NJ) 3 grams/day (lean subjects) or 4 grams/day (obese subjects) in 2 divided doses or identical placebo for ~12 weeks. Study medication will actually be administered over a range of 11 to 13 weeks to accommodate scheduling glitches without impacting any anticipated treatment effects. Subjects and study personnel will be blinded to the treatment assignment. Serum salicylate levels will be measured to assess compliance from a fasting blood sample drawn at baseline (Visit 1) and after 4 weeks (Visit 6), 8 weeks (Visit 7) and 12 weeks (Visit 8) of treatment. Compliance will be defined as salicylate levels being in the therapeutic range for rheumatology practice (10-30 mg/dl) during treatment. A Data and Safety Monitoring Board (DSMB) will keep track of salicylate levels to maintain blinding (see Section 6.0). A fasting lipid profile will also be drawn at baseline (Visit 1) and after 12 weeks (Visit 8) of treatment.

During treatment, all subjects will undergo ovulation monitoring consisting of serum progesterone measurements timed by basal body temperatures along with serial follicular ultrasonography as indicated. After the ~12 weeks of treatment, subjects will undergo repeat testing consisting of an HCG-ST during Visit 8 through 11, a CCT during Visit 11 and a FS-

IVGTT during Visit 12. Visits 8 through 12 will occur during the last week of the study protocol. See Table 1 for an overview of the study protocol and Fig. 2 for the study timeline.

Figure 2

Although it is anticipated that the majority of subjects will undergo the three main test procedures (i.e. HCG-ST, CCT and FS-IVGTT) in the order described, the order in which they will be scheduled may need to be changed to accommodate scheduling glitches, since they will be performed as outpatient procedures in accordance with the CCTS CRC operating hours. The change in order will not impact the integrity of the data.

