- **Salsalate Treatment** – Salsalate use can cause the following adverse effects characteristic of salicylates in descending order of frequency: tinnitus, nausea, hearing impairment, rash and vertigo. These effects are transient, and resolve upon cessation of salsalate. Although cause and effect has not been established, the following less common adverse effects have also been reported: abdominal pain, abnormal hepatic function, anaphylactic shock, angioedema, bronchospasm, decreased creatinine clearance, diarrhea, gastrointestinal irritation, inflammation, bleeding or perforation, hepatitis, hypotension, nephritis, urticaria, myocardial infarction or cerebral vascular accident.

Tinnitus is an expected side effect of salsalate treatment that occurs more frequently at doses higher than the one proposed for this study. To minimize this side effect, subjects will be advised to begin by taking one capsule (i.e. 500 mg of salsalate in subjects receiving salsalate) the first day and increase the dose in one capsule increments every 3 days thereafter until the desired dose is achieved. If tinnitus occurs at any point in the upward dose titration or later on during the treatment, an affected subject will be advised to reduce the daily study medication dose in stepped one capsule increments every 3 days. In a previous study, this approach effectively resolved symptoms enabling subjects to complete the study while still maintaining therapeutic salicylate levels. The nature of any suspicious symptoms reported by a subject will be reviewed to determine whether there is actual tinnitus before the salsalate dose is reduced in the manner described. Vital signs and potential side effects will be monitored every 4 weeks during treatment when subjects report to the CRC to have their blood draw for a salicylate level. Liver function tests, BUN and creatinine levels will be drawn within 4 weeks after study completion to be certain that no lasting untoward hepatic or renal impairment has occurred.

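### The readable protocol schedules no pregnancy test during about 10–13 weeks on study drug, although women already attend at weeks 4 and 8

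*Combined protocol and SAP*

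**What the plan says.** **Tests that are scheduled.** Section 6.1 (Screening) gives the general rule: "Pregnancy will be ruled out in all subjects immediately prior to study testing before and after treatment with salsalate or placebo". Section 6.0 describes the baseline HCG test as "consisting of a single IM HCG injection during Visit 1 after documenting a negative urine pregnancy test". Section 6.1 (Body Composition) adds a spot test before the DEXA scan, which is done once, at study start; there, "If pregnancy test is positive the participant will be excluded". Section 7.0 repeats the conditions for HCG and DEXA.

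**Time on drug.** Section 6.0: "Study medication will actually be administered over a range of 11 to 13 weeks". Salicylate is drawn at baseline and "after 4 weeks (Visit 6), 8 weeks (Visit 7) and 12 weeks (Visit 8) of treatment".

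**What Visits 6 and 7 contain.** Besides the salicylate draw, Section 7.0 says: "Vital signs and potential side effects will be monitored every 4 weeks during treatment when subjects report to the CRC". Section 6.1 (Diet Instruction and Monitoring) has women hand in food records "when they report for each monthly salicylate level blood draw". No pregnancy test is mentioned at either visit.

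**Why pregnancy matters here.** Section 7.0 (Reproductive Risk) classes salsalate as Category C and says the listed risks apply equally to a fetus. Specific Aim 1 in Section 3.0 hypothesises that salsalate induces ovulation.

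**Controls in place.** Sections 4.1 and 7.0 require double-barrier contraception or sterilisation, and Section 4.1 also accepts a non-hormonal IUD. Section 6.1 (Ovulation Monitoring) has every woman chart basal body temperature, with a progesterone draw when the temperature rises.

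**The concern.** The trial gives a drug it expects to restore ovulation to women whose fertility may rise while they take it. It treats exposure in pregnancy as a risk, yet the readable text looks for pregnancy only before the first dose and at the post-treatment work-up. If contraception failed early, no scheduled test would prompt stopping the drug until the course was complete or nearly so.

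A missed period is a weak warning in this population, because oligo/amenorrhea is an entry criterion (Section 4.1). The progesterone step shows that a woman ovulated. Section 6.1 then uses the length of that cycle to time LH testing, and says nothing about what to do if menses does not follow.

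At stake is fetal exposure that two tests at existing visits could shorten. The trial's estimates are not at stake: under the Section 6.1 rule a pregnant woman would not go on to post-treatment testing, whether the pregnancy was found at week 4 or week 12.

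**Working it through.** The plan states no figure for this interval, so there is none to reproduce. The check places each test on the visit calendar.

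**1. Scheduled tests between baseline and post-treatment testing.**
- Visit 1, before HCG (Section 6.0): day 0.
- Before DEXA, done after one of Visits 1–3 (Sections 6.0, 6.1): day 0, 1 or 2.
- Before post-treatment testing (Section 6.1): Visit 8 in the usual order.
- Visits 6 and 7: none in the prose and none in the surviving rows of Table 1.

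Count on treatment before the post-treatment work-up: 0.

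**2. Time on drug before the post-treatment test.**
- Course length: 11 × 7 = 77 days to 13 × 7 = 91 days.
- The text does not say whether dosing ends at Visit 8 or runs through Visits 8–12. At baseline, Visit 4 is at 96 hours (day 4) and "Visit 5 will last ~7 hours and occur 2 days after the CCT", hence day 6. The same spacing puts Visit 12 six days after Visit 8.
- Dosing ends at Visit 8: 77–91 days.
- Dosing runs to Visit 12, with the 11–13 weeks covering the whole course: 77 − 6 = 71 to 91 − 6 = 85 days.
- Overall: 71–91 days. 71/7 = 10.1 and 91/7 = 13, so about 10–13 weeks.

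**3. Test to test.** The first-dose day is not stated. Assumption: day 6 at the earliest, after the baseline FS-IVGTT.
- Shortest: 6 + 71 − 2 = 75 days.
- Longest: 6 + 91 − 0 = 97 days.
- If the HCG test comes last (Section 6.0 lets the order change), first dose is day 4 at the earliest: 4 + 71 = 75 to 4 + 91 = 95 days, inside the same range.
- A later first dose adds day for day.

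**4. With tests at Visits 6 and 7.**
- On drug: 28 days; 56 − 28 = 28 days; then 71 − 56 = 15 to 91 − 56 = 35 days. The longest is 28–35 days.
- Test to test (usual order), the first interval is 6 + 28 − 2 = 32 to 6 + 28 − 0 = 34 days. The longest of the three is then 32–35 days.
- Either way the longest is about 4–5 weeks.

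**5. Number of tests.** 2 × 90 = 180 for completers; 2 × 113 = 226 at the recruitment ceiling in Section 12.2.

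**6. Context: ovulation the plan expects.** Section 12.2 plans on about 10% ovulating on placebo and an increase of 40% on salsalate, with power above 80%. Fisher's exact test with 45 per arm gives 98.7% power for 10% vs 50%, 88.9% for 10% vs 40%, and about 5% for 10% vs 14%. The increase cannot be relative. The plan thus expects 45 × 0.10 = 4.5 ovulating women on placebo and 45 × 0.40 = 18 to 45 × 0.50 = 22.5 on salsalate. This is not a pregnancy forecast: the documents give neither the share who are sexually active nor contraceptive failure rates.

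**The case against.** **The text is incomplete.** Table 1 is damaged, and the appendices and consent form are not reproduced. A test, or an instruction about missed menses, could be there. This stands as a limit: the finding is about the readable text only. If such a test exists elsewhere, Section 6.1 still needs to agree with it.

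**The women are closely followed.** Contraception is mandatory, temperature is charted throughout, progesterone is drawn after a sustained rise, and staff see each woman every four weeks. Using cycle length to time LH testing also implies that the team learns whether menses came. A reader might infer that pregnancy on treatment is unguarded; the documents do not support that. What remains is that prevention and ovulation monitoring do not detect pregnancy.

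**The plan is not silent on consequences.** A reader might infer that exclusion at the DEXA scan is the only consequence of pregnancy. That is too strong. Sections 4.2, 4.3 and 7.0 make pregnancy an exclusion, and the open-ended withdrawal reasons in Section 11.0 include a new medical diagnosis, which could cover it. Still, neither Section 11.0 nor Section 13.3 names pregnancy during treatment or says what then happens.

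**Exact day counts are not warranted.** A single figure such as 83–97 days would assume that Visit 1 is the last baseline test and that dosing ends at Visit 8. The text settles neither, so only the ranges stand.

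**Conclusion.** The point holds as a gap in the safety schedule. In the readable text, about 10–13 weeks on study drug pass without a scheduled pregnancy test, and no action is stated for a pregnancy found on treatment. Tests at the two existing visits would bring the longest interval to about 4–5 weeks.

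These figures rest on the stated 11–13 week course, visits at weeks 4 and 8, and two matters the text leaves open: whether dosing continues through Visits 8–12 and, for test-to-test intervals, the day of first dose. They describe intervals, not a reduction in risk; no number of pregnancies can be derived.

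A reader might also infer that the gap threatens the trial's results. It does not: no endpoint, alpha or power figure depends on it. It is an inexpensive safety improvement that the sponsor should make.

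**What to change.** Amend the Screening paragraph of Section 6.1 to add the urine pregnancy test already in use at Visit 6 (week 4) and Visit 7 (week 8). Add that a positive is repeated once, and that a confirmed positive means stopping study drug and reporting to the DSMB and the IRB. Check that Table 1, the appendices and the consent form agree.

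The cost is two urine tests per woman (180 for 90 completers, at most 226 for 113) and an occasional false positive to repeat. No visit or blood draw is added.

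Two further measures are optional and lie outside this low-cost core. One is a test when a luteal progesterone is not followed by menses within a time fixed in advance. It may not coincide with a visit, so it could need an extra visit or a home kit. The other is following any pregnancy to its outcome, which can run beyond the end of the study.
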